9.4 Long-Term Efficacy Analysis

Assessments to evaluate long-term efficacy will be analyzed for the following measures at each visit until completion of the study

- ACR20/50/70 response rates;
- Change from baseline in individual ACR components;
- Change from baseline in DAS28 (CRP);
- Change from baseline in DAS28 (ESR);
- Change from baseline in CDAI and SDAI;
- Change from baseline in morning stiffness (severity and duration);

- Proportion of subjects achieving LDA and the proportion of subjects achieving CR based on DAS28 (CRP), DAS28 (ESR), SDAI, and CDAI criteria;
- Proportion of subjects with change from baseline in HAQ-DI ≤ -0.3 and ≤ -0.22 , respectively;
- Proportion of subjects with no concomitant corticosteroid use (among subjects with corticosteroid use at baseline);
- ACR/EULAR Boolean remission.

Additionally, assessment for the evaluation of radiographic changes in Period 2 will occur at Week 96 and every 96 weeks thereafter (or Premature Discontinuation visit):

- Change from baseline in modified Total Sharp Score (mTSS);
- Proportion of subjects with no radiographic progression (defined as change from baseline in mTSS of ≤ 0);
- Change from baseline in Radiographic joint space narrowing and joint erosion scores.

Descriptive statistics will be provided for each treatment group sequence as defined in Section 9.1.1. These include the number of observations, mean, standard deviation, 95% CI, median, minimum, Q1, Q3 and maximum for continuous endpoints; and frequencies and percentages with 95% CI using normal approximation for binary endpoints. Plots by treatment group sequence over time up to Week 48 will be provided.

No missing data imputation will be applied. All efficacy analyses will be based on As Observed (AO) analysis.

For Week 26 reporting, long-term efficacy analysis will only be presented up to Week 48.

Table 7 below provides the overview of the long-term efficacy analyses to be performed on different endpoints.

Table 7. Summary of Efficacy Variables and Corresponding Analyses for Long-Term Efficacy Analysis

Efficacy Variables	Analysis Method
Binary Endpoints:	

 • ACR20/50/70 response by visit • LDA and CR based on DAS28(CRP), DAS28 (ESR), SDAI, and CDAI criteria by visit • Proportion of subjects with change from baseline in HAQ-DI ≤ -0.3 and ≤ -0.22, respectively; • Proportion of subjects with no concomitant corticosteroid use (among subjects with corticosteroid use at baseline) • Proportion of subjects with no radiographic progression (defined as change from baseline mTSS of ≤ 0) by visit • Boolean remission 	
 • Point estimate and 95% CI of the response rate for each treatment group sequence • Plot for each treatment group sequence over time • Imputation: AO • Analysis Set: FAS
Continuous Endpoints:	

 • Change from baseline in individual ACR components by visit • Change from baseline in DAS28 (CRP) by visit • Change from baseline in DAS28 (ESR) by visit • Change from baseline in CDAI and SDAI; • Change from baseline in morning stiffness (severity and duration) by visit • Change from baseline in EQ-5D-5L by visit • Change from baseline in RA-WIS by visit • Change from baseline in FACIT-F by visit • Change from baseline in SF-36 by visit • Change from baseline in mTSS by visit • Change from baseline in radiographic joint space narrowing and joint erosion scores by visit 	
 • Point estimate, 95% CI of mean change from baseline together with SD, Min, Q1, Median, Q3 and Max for each treatment group sequence • Plot for each treatment group sequence over time • Imputation: AO • Analysis Set: FAS

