Starting at Week 26 (after Week 26 assessments have been performed) and thereafter, two intra-articular, intramuscular, intravenous, trigger point or tender point, intra-bursa, and intra-tendon sheath injections of corticosteroids, dosage and frequency per standard of care, are allowed. However, joint injections should be avoided within 21 days prior to the next scheduled study visit to avoid confounding effects of systemic absorption of intra-articular corticosteroids. For the analysis of the TJC and SJC, injected joints will be considered "not assessable" for 3 months from the time of the intra-articular injection.

Starting at Week 26 (after Week 26 assessments have been performed) and thereafter, initiation of or change in corticosteroids, NSAIDs, acetaminophen/paracetamol is allowed as per local label. For RA flare treatment, no more than 3 consecutive days of systemic corticosteroids (maximum dose of 0.5 mg/kg/day of prednisone or its equivalent) is allowed, after which subject should resume their usual daily oral corticosteroid dose.

Starting at Week 48 (after Week 48 assessments have been performed) and thereafter initiation of or change in csDMARDs is allowed as per local label (restricted to oral or parenteral MTX, sulfasalazine, hydroxychloroquine, chloroquine and leflunomide, and restricted to concomitant use of up to 2 csDMARDs except the combination of MTX and leflunomide; see Inclusion Criterion 9, Section 5.2.1).

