### 5.3.3.2 Period 2 Variables

Assessments to evaluate efficacy of treatment in Period 2 will be analyzed for the following measures at Weeks 60, 72, 84, 96, and every 12 weeks thereafter until completion of the study:

- ACR20/50/70 response rates;
- Change from baseline in individual ACR components;
- Change from baseline in DAS28 (CRP);
- Change from baseline in DAS28 (ESR);
- Change from baseline in CDAI and SDAI;
- Change from baseline in morning stiffness;
- Proportion of subjects achieving LDA and the proportion of subjects achieving CR based on DAS28 (CRP), DAS28 (ESR), SDAI, and CDAI criteria (as defined for Period 1);
- Proportion of subjects with change from baseline in HAQ-DI  $\leq -0.22$ ;
- Proportion of subjects with change from baseline in HAQ-DI  $\leq -0.3$ ;
- Concomitant corticosteroid use (systemic use and intra-articular injections);
- ACR/EULAR Boolean remission.

Additionally, assessment for the evaluation of radiographic changes in Period 2 will occur at Week 96 and every 96 weeks thereafter (or Premature Discontinuation visit):

- Change from baseline in modified Total Sharp Score (mTSS);
- Proportion of subjects with no radiographic progression (defined as change from baseline in mTSS of  $\leq 0$ );
- Change from baseline in Radiographic joint space narrowing and erosion scores.

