6.1 Demographics and Baseline Characteristics

Demographic and baseline characteristics information will be collected at the Baseline visit of the study and will be summarized for the FAS. The number of observations, mean, standard deviation, median, minimum and maximum will be summarized for continuous variables. Categorical or discrete variables will be summarized via frequencies and percentages. Summary statistics will be computed for each treatment group and overall.

Main Demographic and Baseline Characteristics

- Sex (male/female)
- Age (years)
- Age Categories (< 40, [40, 65), ≥ 65 years)
- Race (White, Black or African American, American Indian or Alaska Native, Native Hawaiian or Other Pacific Islander, Asian, Other)
- Geographic Region (North America, South/Central America, Western Europe, Eastern Europe, Asia, Other)
- Ethnicity (Hispanic or Latino, Not Hispanic or Latino)
- Weight (kg)
- Weight Categories (< 60 kg, ≥ 60 kg)
- Height (cm)
- Body Mass Index (BMI) (kg/m²)
- Body Mass Index (BMI) Category (kg/m²) (BMI < 25 vs BMI ≥ 25)

RA Medical History and Characteristics

- Duration of RA Symptoms in years
- Duration of RA Diagnosis in years
- Duration of RA Diagnosis Categories (< 5 year or ≥ 5 year)
- Prior bDMARD use (Yes or No)
- Oral steroid use at baseline (yes, no)
- Oral steroid dose (prednisone equivalent) at baseline
- MTX dose at baseline
- Baseline MTX dose categories (< 15 mg/week or ≥ 15 mg/week)

ACR and/or DAS Components at Baseline

- Tender joint count (TJC68) defined as the number of tender joints out of 68 assessed joints

- Swollen joint count (SJC66) defined as the number of swollen joints out of 66 assessed joints
- Tender joint count (TJC28) defined as the number of tender joints out of 28 assessed joints used for DAS28 calculation
- Swollen joint count (SJC28) defined as the number of swollen joints out of 28 assessed joints used for DAS28 calculation
- Physician's global assessment of disease activity (mm on a 100-mm horizontal visual analogue scale [VAS])
- Patient's assessment of pain within last week (mm on a 100-mm horizontal (VAS)
- Patient's global assessment of disease activity within last 24 hours (mm on a 100-mm horizontal VAS)
- Health Assessment Questionnaire Disability Index of the (HAQ – DI) (range: 0 to 3)
- High sensitivity C-reactive protein (hsCRP) (mg/L)
- Erythrocyte sedimentation rate (ESR) (mm/hr)

Other Baseline RA Disease Characteristics

- Anti-cyclic citrulliated peptide (Anti-CCP) (units)

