6.3 Prior Treatment and Concomitant Medications

Prior and concomitant medications will be summarized by each randomized treatment groups as well as overall for FAS. Prior medications are those medications taken prior to the first dose of study drug. This includes medications with a start date before the first study drug administration date, regardless of the end date of these medications. Medications taken on the day of the first dose of study drug are not counted as prior medications. Concomitant medications are those medications, other than study drug, taken after the first dose of study drug and within 14 days of the last dose of study drug. This includes medications with a start date between first study drug administration and last study drug administration + 14 days, as well as, medications with a start date prior to first dose of study drug and which are ongoing after first dose of study drug. Medications taken on the day of the first dose of study drug are counted as concomitant medications.

The number and percentage of subjects who received a prior medication and the number and percentage of subjects who received a concomitant medication will be tabulated separately by the generic name assigned by the most current version of the World Health Organization (WHO) Drug Dictionary.

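### The SAP's long-term corticosteroid variable covers only baseline users who are off steroids, so it cannot show the new use and injections that the protocol's variable includes

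*SAP*

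**What the plan says.** Protocol 5.3.3.2 includes among the Period 2 efficacy measures "Concomitant corticosteroid use (systemic use and intra-articular injections". The synopsis has the same item. Neither limits it to subjects who were on steroids at baseline. Protocol 8.1.4.2 says the endpoints in 5.3.3.2 will be summarized for all visits.

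SAP 9.4 gives the corresponding item as "Proportion of subjects with no concomitant corticosteroid use (among subjects with corticosteroid use at baseline", and Table 7 repeats it. The analysis is As Observed, descriptive and by treatment group sequence. Neither place mentions systemic or intra-articular use, says what counts as use, or explains the change from the protocol. The only steroid status that SAP 6.1 lists as a baseline yes/no characteristic is "Oral steroid use at baseline (yes, no".

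Protocol 5.2.3.1 relaxes the steroid rules after the Week 26 assessments. From then on "initiation of or change in corticosteroids, NSAIDs, acetaminophen/paracetamol is allowed as per local label", and so are "two intra-articular, intramuscular, intravenous, trigger point or tender point, intra-bursa, and intra-tendon sheath injections of corticosteroids". Neither permission depends on baseline steroid status.

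Outside the efficacy section, SAP 6.3 says "Prior and concomitant medications will be summarized by each randomized treatment groups as well as overall for FAS", and that "the number and percentage of subjects who received a concomitant medication will be tabulated separately by the generic name".

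**The concern.** The protocol asks how much corticosteroid subjects use in the long term. The SAP asks how many baseline users are off it. These differ in direction (use against non-use), in denominator (all subjects against baseline users) and in content (the systemic and intra-articular elements are gone).

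Take a subject who was not on steroids at baseline, starts prednisone after Week 26 and has two joint injections. That subject is a user under the protocol's variable and is absent from the SAP's. A baseline user who stops is counted in the SAP's numerator. One direction of change is visible and the other is not.

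This matters for reading the rest of SAP 9.4. The long-term response rates there are As Observed, so responses reached after a steroid start are counted as they stand. Steroid use by visit in all subjects is the context a reader needs beside those rates, and the long-term section does not supply it.

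**Working it through.** The plan states no rate, power or sample size for this variable, so there is no figure to reproduce. The check has three parts.

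**1. Is either text superseded?** The protocol synopsis is dated 01 December 2017 and SAP Version 2 is dated 07 December 2017. Both are current, and SAP 3.0 describes itself as elaborating on the protocol's methods.

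**2. Does another SAP output restore the protocol's variable?** SAP 6.3 defines concomitant medication to take in new starts: "This includes medications with a start date between first study drug administration and last study drug administration + 14 days". New steroid use and injections in baseline non-users are therefore counted there. The same definition also takes in drugs begun before the first dose and still ongoing, so starters and continuing users are pooled. The table is by generic name and randomized group. No visit or route is stated. Randomized group mixes study drugs after switching: every remaining placebo subject moves to upadacitinib at Week 26, and non-responders cross between upadacitinib and adalimumab. The efficacy tables in SAP 9.4 are by treatment sequence. So 6.3 records the drugs but does not give the view the protocol asks for.

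**3. What does the SAP measure respond to?** Let b be the share of subjects on steroids at baseline, s the share of baseline users off steroids at a visit, and q the share of baseline non-users on steroids at that visit. Assume the same subjects are observed at both times.

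- SAP measure = s
- Use in all subjects = b(1 − s) + (1 − b)q
- Change from baseline = (1 − b)q − bs
- Use rises when q > bs/(1 − b)

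The SAP measure does not contain q. The documents give none of b, s or q, so the values below are assumptions shown over a range, with s = 20%:

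| b | q | SAP measure | Use in all subjects | Change (points) |
|---|---|---|---|---|
| 30% | 0% | 20% | 24% | −6 |
| 30% | 20% | 20% | 38% | +8 |
| 30% | 40% | 20% | 52% | +22 |
| 50% | 0% | 20% | 40% | −10 |
| 50% | 20% | 20% | 50% | 0 |
| 50% | 40% | 20% | 60% | +10 |
| 70% | 0% | 20% | 56% | −14 |
| 70% | 20% | 20% | 62% | −8 |
| 70% | 40% | 20% | 68% | −2 |

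For the second row: 0.30 × 0.80 + 0.70 × 0.20 = 0.24 + 0.14 = 0.38.

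The q at which use neither rises nor falls is:

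- b = 30%: 0.06/0.70 = 8.6%
- b = 50%: 0.10/0.50 = 20%
- b = 70%: 0.14/0.30 = 46.7%

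If no baseline user stops (s = 0) and q = 40%, the SAP measure reads 0%, while use rises by 0.70 × 0.40 = 28 points at b = 30% and by 0.30 × 0.40 = 12 points at b = 70%.

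**The case against.** A fair defence has several parts.

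- Protocol 5.3.3.2 gives no statistic, denominator or look-back interval, and Protocol 8.1 leaves details to the SAP. That is true, but choosing a statistic is different from dropping baseline non-users and the named intra-articular element.
- Restricting a non-use proportion to baseline users is sensible in itself, since including non-users would inflate it. It is also strict, because tapering without stopping earns no credit. This stands, and it is a reason to keep the measure as a subset analysis.
- Protocol 5.2.3.1 limits the effect of steroids on joint assessments. It allows two injections, asks that joint injections be avoided in the 21 days before a visit, treats injected joints as not assessable for 3 months, and caps systemic flare treatment at 3 consecutive days. These rules reduce the effect on response rates but do not report how much steroid was used.
- The variable is descriptive and untested. This stands and limits the weight of the point.

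A reader might also infer three stronger things that the documents do not support.

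- That new starts and injections disappear from the SAP. They do not; SAP 6.3 counts them.
- That the measure can only look like steroid sparing. It can stay at 0%, fall between visits if subjects restart, or be worse in one treatment sequence than in another. Starting from 0% is not peculiar to it, since the ACR responder rates in the same list do so too.
- That it overstates the fall in use by a calculable amount. With 60% baseline users, 20% of them stopping and 10% of non-users starting, all-subject use is 0.60 × 0.80 + 0.40 × 0.10 = 52%, against the 48% obtained from stoppers alone. But the SAP never multiplies its proportion into a prevalence. It reports a share of baseline users, labelled as such, and the rates in the example are invented.

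**Conclusion.** The point holds as a mismatch between protocol and SAP. A Period 2 efficacy variable that the protocol lists without restriction is replaced, without explanation, by one that cannot register new systemic use or injections in baseline non-users. The replacement can show a reduction from baseline but never a net increase. This follows from the two definitions and does not depend on any assumed rate.

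The size of the resulting difference does depend on rates the documents do not give. Across the values tried, a SAP figure of 20% is compatible with all-subject use falling by 14 points or rising by 22.

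The consequence is modest. No primary, ranked or tested result is touched, and the drugs concerned still appear in the general medication table. A separate loose end is that SAP 9.4 does not define use or use at baseline. Inhaled steroids are permitted and SAP 6.1 lists only oral use, so membership of the denominator is unsettled. The change is worth making because it restores a summary that the protocol promises.

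**What to change.** In SAP 9.4 and Table 7, add by visit and treatment sequence:

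- the proportion of all subjects with systemic corticosteroid use;
- the proportion of all subjects with an intra-articular injection;
- the proportion with new use among subjects not on corticosteroids at baseline.

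Keep the existing proportion, labelled as a subset analysis of baseline users. State the look-back interval for each visit; the protocol sets none, so the SAP has to choose one. Define use and use at baseline by route, so that inhaled use does not count in either.

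The cost is SAP wording and one added descriptive table. Protocol 5.2.3 already requires dose, route and start and end dates for every medication, so no new data are needed. The reported reduction in steroid use may look less favourable once new use is shown beside it.

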#### **Upadacitinib:**

- Subjects who do not achieve a  $\geq 20\%$  improvement in TJC and SJC at Weeks 14, 18, or 22 compared to baseline will be switched to blinded ADA treatment.
- At Week 26, all remaining subjects who do not achieve LDA according to CDAI (LDA defined as  $CDAI \leq 10$ ) at Week 26 will be switched to blinded ADA treatment.

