Subjects must have been on oral or parenteral MTX therapy for ≥ 3 months, on a stable MTX dose for ≥ 4 weeks prior to the first dose of study drug (15 to 25 mg/week; or ≥ 10 mg/week in subjects who are intolerant of MTX at doses ≥ 12.5 mg/week), and must remain on a stable dose throughout the study; the MTX dose may be decreased only for safety reasons. In addition, all subjects should take a dietary supplement of oral folic acid (or equivalent) throughout study participation. Folic acid dosing and timing of regimen should be followed according to the Investigator's instructions. Starting at the Week 26 visit (after Week 26 assessments have been performed) and thereafter, initiation of or change in background RA medication(s) including, corticosteroids, non-steroidal anti-inflammatory drugs (NSAIDs), acetaminophen/paracetamol is allowed as per local label. Starting at Week 48 (after Week 48 assessments have been performed) and thereafter, initiation of or change in csDMARDs is allowed as per local label (restricted to oral or parenteral MTX, sulfasalazine, hydroxychloroquine, chloroquine and leflunomide, and restricted to concomitant use of up to 2 csDMARDs except the combination of MTX and leflunomide).

Starting at the Week 48 and thereafter, at least 20% improvement in BOTH TJC AND SJC compared to baseline is required to remain on study drug. Anyone who does not fulfill this criterion at 2 consecutive visits (starting at Week 48) must be discontinued from study drug.

Subjects with prior exposure to at most one biologic disease-modifying anti-rheumatic drug (bDMARD) (except ADA) for RA may be enrolled in the study (up to 20% of total number of subjects) after the required washout period is satisfied and if they have a) limited bDMARD exposure (< 3 months), OR b) response to a bDMARD but had to

discontinue that bDMARD due to intolerability (regardless of treatment duration) (for washout periods. These subjects will be equally stratified across all treatment groups. Subjects, who are considered bDMARD-inadequate responders (lack of efficacy), as determined by the Investigator, are not eligible.

Rescue therapy will be offered to subjects who meet the following criteria:

Placebo:

- Subjects who do not achieve a $\geq 20\%$ improvement in TJC and SJC at Weeks 14, 18, or 22 compared to baseline will be switched to blinded Upadacitinib treatment.

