- At Week 26, all remaining subjects will be switched to blinded Upadacitinib treatment regardless of clinical response.

ADA:

- Subjects who do not achieve a $\geq 20\%$ improvement in TJC and SJC at Weeks 14, 18, or 22 compared to baseline will be switched to blinded Upadacitinib treatment.
- At Week 26, all remaining subjects who do not achieve LDA according to CDAI (LDA defined as $CDAI \leq 10$) at Week 26 will be switched to blinded Upadacitinib treatment.

Upadacitinib:

- Subjects who do not achieve a $\geq 20\%$ improvement in TJC and SJC at Weeks 14, 18, or 22 compared to baseline will be switched to blinded ADA treatment.
- At Week 26, all remaining subjects who do not achieve LDA according to CDAI (LDA defined as $CDAI \leq 10$) at Week 26 will be switched to blinded ADA treatment.

An unblinded analysis will be conducted after all subjects have completed Week 26 for the purpose of regulatory submission. To maintain integrity of the trial and avoid introduction of bias, study sites and subjects will remain blinded for the duration of Period 1. Additional unblinded analyses may be conducted after the Week 26 unblinded analysis for regulatory purposes.

Each subject will undergo a maximum of 5 scheduled visits for x-ray examination of bilateral hands and feet during Period 1 (unless unscheduled repeat imaging is needed due to failure to meet the quality requirements) at Screening, Week 26, and Week 48/Premature Discontinuation. Subjects who are non-responders (defined as those not achieving $\geq 20\%$ improvement in TJC and SJC criterion) at Week 14 and are switched to rescue therapy will have an x-ray examination at Week 14; in addition, subjects who prematurely discontinue from study drug or the study [REDACTED] will have an x-ray examination at the premature discontinuation timepoint (refer to protocol for additional details).

[figure not shown]
Joint x-rays will be sent to the central imaging vendor designated by the Sponsor. The x-rays will only be assessed by the imaging vendor for joint erosions and joint space narrowing, and will not be assessed for any other clinically significant findings that may impact a subject's health.

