9.1.1 Efficacy Analysis at Different Phases of the Study

Efficacy Analysis by Week 12

Standard efficacy analysis by randomized treatment groups (placebo, ADA 40 mg EOW and Upadacitinib 15 mg QD) will be performed on efficacy data up to Week 12. No protocol-defined treatment switching will occur prior to the time point. Formal statistical inference will be generated, and results from this set of analysis will be used as the key efficacy findings of this study.

Efficacy Analysis for Period 1

For visits at Weeks 14, 18, 22, or 26, subjects may have switched to a treatment that is different from their originally randomized treatment group due to lack of efficacy. At Week 26, all remaining subjects in the original placebo group will be switched to blinded ABT-494 treatment regardless of clinical response. For treatment group comparison purposes, appropriate approaches will be applied to assessments that occur after the time of such treatment switching. For Week 26 reporting, this set of analyses will only be presented up to Week 26.

Long-Term Efficacy Analysis

Long-term efficacy analysis will be performed on As Observed data (defined in Section 9.1.2) by treatment group sequence as described below. There will be no statistical testing; only descriptive statistics and confidence intervals will be provided. For Week 26 reporting, this set of analyses will only be presented up to Week 48.

1. Placebo → Upadacitinib 15 mg QD
2. ADA 40 mg EOW
3. ADA 40 mg EOW → Upadacitinib 15 mg QD
4. Upadacitinib 15 mg QD
5. Upadacitinib 15 mg QD → ADA 40 mg EOW

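### Long-term efficacy is tabulated only by treatment sequence, and in the two active arms the sequence is itself set by response, so the tables do not isolate a drug effect

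*SAP*

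**What the plan says.** **Grouping.** SAP 9.1.1: "Long-term efficacy analysis will be performed on As Observed data (defined in Section 9.1.2) by treatment group sequence as described below". Five sequences are listed: placebo to upadacitinib, ADA, ADA to upadacitinib, upadacitinib, and upadacitinib to ADA. The status of these tables is also stated there: "There will be no statistical testing; only descriptive statistics and confidence intervals will be provided". SAP 9.4 repeats the grouping: "Descriptive statistics will be provided for each treatment group sequence as defined in Section 9.1.1". It adds: "Plots by treatment group sequence over time up to Week 48 will be provided".

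**What decides the sequence.** The first rule looks at joint counts. SAP 4.2 says, for placebo and ADA subjects short of the 20% threshold: "improvement in TJC and SJC at Weeks 14, 18, or 22 compared to baseline will be switched to blinded Upadacitinib treatment". The upadacitinib arm has the same rule with ADA as the second drug. The second rule, in Protocol 5.2.3.3 for the upadacitinib arm, covers "At Week 26, all remaining subjects who do not achieve LDA according to CDAI", with LDA meaning CDAI of 10 or below; these subjects switch. The ADA arm has the mirror rule. Placebo differs: "At Week 26, all remaining subjects will be switched to blinded Upadacitinib treatment regardless of clinical response".

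**What is tabulated.** SAP Table 7 lists, within each sequence, "LDA and CR based on DAS28(CRP), DAS28 (ESR), SDAI, and CDAI criteria by visit". SAP 9.5.10 sets the CDAI LDA cut-off at 10, the same as the switching cut-off.

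**What exists by randomised group.** SAP 9.3.1 plans analyses with rescue handling, and As Observed summaries, over Period 1. In the Week 26 report that set stops at Week 26, while the sequence tables run to Week 48. After Week 48 only the sequence tables remain.

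**The concern.** One CDAI reading at Week 26 does two jobs. It sorts active-arm subjects into sequences, and it is one of the outcomes reported for those sequences. Nothing in SAP 9.4 tells the reader so. Three consequences follow.

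- At Week 26 the CDAI LDA rates of on-drug subjects in the unswitched sequences, and of those switched that week, are fixed by the rule whatever the drug does.
- At earlier visits the plots group subjects by something that happens later.
- At later visits, subjects grouped by a noisy reading drift back towards their usual level. In the switched sequences this looks like benefit from the second drug. In the unswitched sequences it looks like loss of response.

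Protocol 5.6.1 says the extension will allow maintenance of response to both drugs to be assessed, and these are the tables that would carry that statement. The placebo-to-upadacitinib sequence is not selected on response at Week 26, so setting it beside unswitched upadacitinib compares an unselected group with a selected one.

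**Working it through.** **1. The plan's own figure.** The documents give no expected long-term response rate. The only LDA rates are in SAP 4.3: 35% for ADA and 40% for upadacitinib, DAS28(CRP) at Week 12, used for non-inferiority with a 10% margin. With 10% dropout (540 against 270):

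SE = √(0.35×0.65/270 + 0.40×0.60/540) = 0.0359; power = Φ(0.15/0.0359 − 1.96) = 98.7%.

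This agrees with the stated minimum of 90% and is not in dispute. Below, 35% and 40% serve only as stand-ins for the Week 26 CDAI LDA rate.

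**2. Week 26, from the text alone.** On study drug, active arms, handled per protocol:

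| Subject at Week 26 | Sequence | CDAI LDA at Week 26 |
|---|---|---|
| CDAI ≤ 10, not rescued earlier | unswitched | 100% |
| CDAI > 10, not rescued earlier | switched at Week 26 | 0% |
| Rescued at Weeks 14 to 22 | switched earlier | not fixed |

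No assumption is needed here.

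**3. Next visit, no effect of switching (model A).** Assumptions, none in the documents: true CDAI lognormal, median 9, 12 or 16, log SD 0.7; visit-to-visit SD 2, 3, 4 or 6 points, floored at 0; the true value unchanged between visits; 1,000,000 simulated subjects per scenario.

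| Group at Week 26 | Week 26 | Next visit, all scenarios | Next visit, median 12, SD 3–4 |
|---|---|---|---|
| Switched (CDAI > 10) | 0% | 6.6% to 32.0% | 14% to 18% |
| Unswitched (CDAI ≤ 10) | 100% | 56.3% to 88.3% | 71% to 77% |

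Without the grouping, the rate is the same at both visits.

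**4. Second model (model B).** CDAI at two visits is bivariate normal with correlation ρ (assumed, 0.6 to 0.9) and the same LDA rate p at both.

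| p | ρ | LDA later, if LDA at Week 26 | LDA later, if not |
|---|---|---|---|
| 0.40 | 0.6 | 64.4% | 23.8% |
| 0.40 | 0.7 | 69.4% | 20.4% |
| 0.40 | 0.9 | 82.6% | 11.6% |
| 0.35 | 0.6 | 61.1% | 21.0% |
| 0.35 | 0.9 | 81.0% | 10.2% |

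Check at p = 0.40, ρ = 0.7: 0.40×0.694 + 0.60×0.204 = 0.278 + 0.122 = 0.40. The randomised group stays at 40% while the two subgroups move in opposite directions. Adding an early-rescue step that removes 10 to 20% of subjects hardly changes the later rates. It lifts the Week 26 rate among all switched subjects to between 0 and 3%, because early switchers can reach LDA by then.

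**5. Subjects off study drug.** SAP 4.2 exempts them from the Week 26 rule, and As Observed (SAP 9.1.2) keeps their data. SAP 9.4 does not say which sequence they join. Suppose 10% are off drug before Week 26 and any who stay in the study are counted as unswitched. For upadacitinib, 540 are on drug and 216 (40%) are in LDA.

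- All 60 stay, none in LDA: 216/(216+60) = 78.3%.
- 15 stay, 40% in LDA: (216+6)/(216+15) = 96.1%.

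For ADA (270 on drug, 94.5 in LDA at 35%), 30 staying with none in LDA gives 94.5/124.5 = 75.9%. With these exceptions the tabulated Week 26 rate could be about 76 to 96% rather than 100%.

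**The case against.** **The tables are descriptive.** SAP 9.1.1 makes the Week 12 analyses the key findings and rules out testing here. This stands, and it limits the consequence to how tables, confidence intervals and plots are read.

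**Randomised-group summaries already exist.** SAP 9.3.1 covers the same clinical endpoints to Week 48, with rescue handling and As Observed. This stands for Period 1. It does not cover Period 2, or the weeks after Week 26 in the Week 26 report.

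**No objective asks how well a switch works.** True: the Period 2 objective is long-term safety, tolerability and efficacy. Maintenance of response is named in Protocol 5.6.1, however, and the unswitched sequences are where it would be read.

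**The sizes rest on assumed inputs.** They do, and the switched range is nearly fivefold. The direction does not depend on them: any imperfect correlation between visits produces it. No size is offered for the joint-count switches, because ACR20 also needs three of five other measures.

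**Stronger readings that a reader might infer.** One is that the unswitched arms show 100% generally. The rule fixes only CDAI LDA, only at Week 26, and only for on-drug active-arm subjects. Off-drug subjects are exempt, and small mismatches can arise because the switch uses the CDAI calculated by the IRT while the tables use windowed values (SAP 5.2). Another is that noise explains all responders after a switch. Noise is enough to produce some; the documents cannot show that it produces all.

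**Conclusion.** The point holds for the long-term tables in the ADA and upadacitinib arms. Sequence membership is defined by outcome, Week 26 CDAI LDA is fixed by rule for on-drug subjects, and earlier visits are conditioned on later response. With no switching effect, model A gives 7 to 32% apparent LDA at the next visit after a Week 26 switch and a fall from 100% to 56 to 88% in unswitched subjects. Model B gives 10 to 24% and 61 to 83%. Both rest on assumed visit-to-visit variability and a constant true level.

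The sequence figures therefore do not isolate a drug effect, which is not the same as saying that they contain none. The documents give no ground for extending the point to the primary or ranked endpoints, the power statements or type I error, since none of these uses the sequences.

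**What to change.** In SAP 9.4 and Table 7:

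(a) Extend the As Observed descriptive summary by randomised group from 9.3.1 into Period 2, and show it beside the sequence tables wherever they appear, including the post-Week 26 data in the Week 26 report. It describes starting on each drug and following the switching rules, not that drug alone, and it remains open to dropout. It has no selection through the switching rule.

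(b) Mark Week 26 CDAI LDA in the ADA and upadacitinib sequences as fixed by the switching rule for on-drug subjects. State that these sequences are outcome-defined and that pre-switch visits are conditioned on later response.

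Two other remedies may suggest themselves and are not recommended. Change from the switch-visit value starts from a reading selected for being above 10; in model A with no effect it averages −0.2 to −3.1 points. Requiring response at two consecutive visits still leaves 3 to 18% apparent responders and puts two response definitions side by side.

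The cost is SAP wording and extra descriptive tables from data already collected. The long-term rates by randomised group will look less favourable than those in the unswitched sequences. No change to the rescue rules is proposed.
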